## 13.3 Reporting Plans

The Principal Investigator at BMC/BU Medical Campus will report Unanticipated Problems, safety monitors' reports, and Adverse Events to the BMC/BU Medical Center IRB in accordance with IRB policies:

- Unanticipated Problems occurring at BMC/BU Medical Campus will be reported to the BMC/BU Medical Campus IRB within 7 days of the investigator learning of the event.
- Adverse Events (including Serious Adverse Events) will be reported in summary at the time of continuing review, along with a statement that the pattern of adverse events, in total, does not suggest that the research places subjects or others at a greater risk of harm than was previously known.
- Reports from safety monitors with recommended changes will be reported to the IRB within 7 days of the investigator receiving the report.
- Reports from safety monitors with no recommended changes will be reported to the IRB at the time of continuing review.

### 13.4 Stopping Rules

The study has no pre-defined stopping rules.

## 14 Data Handling and Record Keeping

### 14.1 Confidentiality

All data will be collected for research purposes and all records will be stored in locked filing cabinets or password protected computers accessible only to research staff. Research data will be collected and stored using subject IDs rather than participant names or other direct identifiers such as medical record number. Any paper copies will be kept in locked offices. Electronic files containing any identifiable information (such as the study key) will be password protected and only research staff will have access to the password. The study key will be kept separate from the study data (assessments and audio recordings). Files containing audio-recordings of participants will be password protected as well.

Study data collected by research study staff during research interviews in private locations. Study data collected by research study staff includes baseline and follow-up interview data. All research interview data will be entered into REDCap, managed by BEDAC. REDCap is a secure, web application designed to support data capture for research studies, providing user-friendly web-based case report forms, real-time data entry validation (e.g. for data types and range checks), audit trails, and data export mechanism to common statistical packages (SPSS, SAS, Stata, R/S-Plus). The system was developed by a multi-institutional consortium and was initiated at Vanderbilt University. The REDCap is hosted on a computer network exploitation -based server. Network transmissions (data entry, survey submission, web browsing, etc.) in REDCap are protected via Secure Sockets Layer (SSL) encryption. Access to REDCap can be restricted at different levels (e.g., research assistant, PI, and Co-Investigators). Exported data from REDCap will be stored on the Boston University Medical Campus' secure password-protected server.

Audio-recordings of intervention sessions with participants will be uploaded and stored on a secure, HIPAA compliant server (e.g., DropBox, Box.com, SharePoint, etc). A study ID will be used to identify the recordings. They are not connected with the primary study database in any way.

## 14.2 Study Documentation, Source Data, and Case Report Forms (CRFs)

Data sources in the study include pre-screening data collected via BuildClinical, the phone screening data, baseline, 1-, 2-, 3-, 5-, 6-, 9- and 12-month assessment data to be collected via phone or in-person and input into REDCap by study staff, medical record data, and, audio-recordings.

Screening information collected via BuildClinical will be housed securely in BuildClinical's online platform. Screening information on potentially eligible participants collected by BU study staff will be housed securely in REDCap.

The phone screen and study baseline and follow-up interview data will be collected verbally from the participant to study staff over the phone, and directly entered by research staff into REDCap case report forms, and stored electronically in REDCap. Information collected during the phone screening is collected to determine eligibility for the study. Research interviews will collect information on demographic variables, health and medical status, symptoms of anxiety and depression, pain, recent medical appointments, current medications, knowledge of opioids, pain treatments, physical activity, substance use, psychosocial functioning, experience of discrimination, satisfaction with the intervention, and more. Data collected at the follow up time points are to understand change over time, especially after the intervention period.

RAs conducted medical chart reviews from participants who were recruited from the two primary care, office-based addiction treatment (OBAT) buprenorphine clinics in New England to collect data on buprenorphine retention at 6- and 12-months post-enrollment.

Corrections on data collection forms: If any entry error has been made to hardcopy data collection forms, to correct such an error, a single straight line will be drawn through the incorrect entry and the correct data will be entered above it. All such changes will be initialed and dated. There will be no erasures or white-out on CRFs. For clarification of illegible or uncertain entries, the clarification will be printed above the item, then initialed and dated.

## 14.3 Study Records Retention

All study records (e.g., informed consent, REDCap survey records, intervention session recordings, etc.) from this trial will be retained for a minimum of seven years after the study is completed per Boston Medical Center and Boston University requirements. Data stored in REDCap will be managed and retained by study staff. Hard copy documents will be stored in locked filing cabinets. After the seven years of required data retention, the study PI will determine when the information can be destroyed.

# 15 Statistical Plan

## 15.1 Study Hypotheses

1. Participants in the TOPPS intervention, compared to Health Education, will report less pain interference and pain severity over the 3-month treatment phase.

2. Participants in the TOPPS intervention, compared to Health Education, will report fewer depressive symptoms over the 3-month treatment phase.
3. The TOPPS intervention, compared to HE, will result in sustained improvements in pain interference, pain severity, depressive symptoms and buprenorphine treatment retention over the study period.

Examining mechanisms by which TOPPS may reduce pain interference. Proposed mechanisms include: 1) (increased) steps per day (as a measure of general physical activity level); 2) (increased) activities engagement; 3) (decreased) avoidance of meaningful life activities; and 4) (decreased) fear of pain.

## 15.2 Sample Size Determination

We plan to recruit 125 subjects to each study condition. Based on an attrition rate of 20% we anticipate having approximately 100 participants per condition available for analysis. Our primary power calculations are based on Aim 1. Based on the literature [17-19], we determined that a minimally significant difference between treatment groups on outcomes would be a standardized mean difference (SMD) of at least 0.4 at 3 months. Assuming  $\alpha/2 = 0.05$ , we need 99 subjects per arm to detect an SMD of 0.4 with  $1-\beta = 0.8$ . Thus, the proposed design has sufficient power to detect small-moderate effects for Aims 1 and 2.

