## 2 Protocol Summary

Title:	Treating Opioid Patients' Pain and Sadness (TOPPS)
Population:	163 participants currently being treated with buprenorphine

Intervention:	Intervention: 12-week lifestyle psychoeducation about pain, depression, and opioid use; as well as values-based, behavioral activation to increase engagement in meaningful activities. Timing: 3-months Method: Randomized controlled trial
Objectives:	1) to determine whether the TOPPS intervention, compared to HE, results in less pain interference and pain severity over the 3-month treatment phase; 2) to determine whether TOPPS, compared to HE, results in less depressive symptoms over 3 months; 3) to determine whether TOPPS, compared to HE, results in sustained improvements in pain interferences, pain severity, depressive symptoms, and buprenorphine treatment retention (self-reported continuous treatment) over the 12 months of the study.
Design/Methodology:	163 participants who are currently being treated with buprenorphine and who endorse pain and depressive symptoms were randomized into the trial. Recruitment occurred from two primary care, office-based addiction treatment (OBAT) buprenorphine clinics, as well as through online advertisement. Following consent and the baseline interview, participants were randomized to one of two study arms: the TOPPS intervention or health education. The TOPPS intervention consists of 3 main components: 1) psychoeducation about pain, depression, opioid use, their interactions, and the role of avoidance; 2) coaching in how to be an informed, activated patient; and 3) values-based, behavioral activation, to increase engagement in meaningful activities. The intervention is a total of 6 phone-based sessions over 12 weeks with a Behavioral Health Specialist (BHS). The control arm (health education) involves six sessions led by the same BHS. The first health education session is titled "What to Eat." Participants then select five additional topics, one for each of the remaining sessions. Topics include, "What Not to Eat," "Colds, Germs, and Flu," "Preventing Cancer," "Diabetes," "Protecting your heart," "Getting a Good Night's Sleep," "Complementary and Alternative Medicine (CAM)," "Caffeine," and "Physical Activity." Follow-up interviews are conducted by trained Research Assistants (RAs) at 1, 2-, 3-, 6-, 9-, and 12-months (for participants enrolled prior to XX) post-enrollment.
Total Study Duration:	5 years

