## 15.3 Statistical Methods

We will present descriptive statistics. Random effects logistic regression will be used to determine if treatment condition, demographic characteristics, or baseline outcome measures predict study attrition. Any variables that significantly ( $p < .10$ ) predict study attrition will be included in multiple imputation models and as covariates in multivariate models testing the effects of intervention. Graphical methods will be used to evaluate the distributions of outcome variables, examine model residuals, describe change in outcomes over time, and guide the specification generalized linear mixed models testing intervention effects. A 2-tailed probability of Type I error  $< 0.05$  will be used for all null hypothesis tests. Missing data due to participant attrition and item non-response is inevitable. We will conduct intent-to-treat analysis using multiple imputation by chained equation (MICE) to generate fully populated data sets [20]. More specifically we will use the mi impute and mi estimate facilities in Stata 17 to generate and analyze the fully populated data files [21]. The number of imputed data sets will be determined by using the how many imputations procedure [22]. MICE is a flexible tool that allows imputing values for outcomes with a range of distributions (e.g., continuous, dichotomous, count, etc.). MICE assume data are missing at random (MAR) (e.g., missing is random conditional on variables in the imputation model). Variables used in the imputation models will include treatment assignment, all observed instances of the outcome being imputed, and any additional baseline variables found to significantly ( $p < .10$ ) predict subject attrition using mixed-effects logistic regression. Including baseline predictors of attrition supports the MAR assumption.

The BPI, the VAS pain severity scales (worst and average in last week), and the PHQ-9 will be administered at baseline and at all follow-up assessments. The effect of intervention on pain interference (BPI-I), pain severity, and depressive symptoms during the 3-month treatment phase will be evaluated in a generalized linear mixed model framework using the fully populated data sets generated by MICE. Models will include baseline pain and PHQ-9 depression measures as covariates. All available panel data will be included in the model to support the efficiency of estimation. Time specific estimates

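### Section 15.2 claims 80% power from 125 per arm, but 163 were randomised in total: on the plan's own assumptions power at SMD 0.4 is about 62%, and the alpha is misprinted

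*Combined protocol and SAP*

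**What the plan says.** Section 15.2 gives the recruitment target as "We plan to recruit 125 subjects to each study condition". It continues: "Based on an attrition rate of 20% we anticipate having approximately 100 participants per condition available for analysis". The difference judged to matter is a "standardized mean difference (SMD) of at least 0.4 at 3 months". With alpha/2 written as 0.05 and power of 0.8, it states that "we need 99 subjects per arm to detect an SMD of 0.4 with" that power, and ends: "Thus, the proposed design has sufficient power to detect small-moderate effects for Aims 1 and 2".

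Section 2 (Protocol Summary) gives the population as 163 and reports in the past tense: "163 participants who are currently being treated with buprenorphine and who endorse pain and depressive symptoms were randomized into the trial". Section 5 sets 1:1 allocation.

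Section 15.3 sets the test level: "A 2-tailed probability of Type I error" below 0.05 "will be used for all null hypothesis tests".

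**The concern.** The same current document gives a target of 250 and an achieved total of 163. The power conclusion is attached to the target only. Before any loss to follow-up, 163 split 1:1 is 81.5 per arm, already short of the 99 that Section 15.2 says it needs. Nothing explains the shortfall, restates the power, or labels Section 15.2 as the original, unmet plan.

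The claim covers Aims 1 and 2, so it includes the primary pain outcomes, and SMD 0.4 is the plan's own minimally significant difference. A reader who accepts 80% power may take a null result as good evidence against a difference of that size, when the chance of missing it was materially higher than 20%.

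A second, smaller problem lies in the same paragraph. Read literally, alpha/2 = 0.05 is a two-sided 10% test, which conflicts with Section 15.3 and does not produce 99.

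**Working it through.** **Inputs.** SMD 0.4, power 0.80, 20% attrition, 125 planned per arm, 99 needed per arm (Section 15.2); two-sided 5% (Section 15.3); 163 randomised (Section 2); 1:1 allocation (Section 5). The documents give neither the split by arm nor the actual attrition, so equal arms are assumed and attrition is varied.

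**1. Reproduce the stated 99.** n per arm = 2(z_alpha + z_beta)² / SMD².

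- Two-sided 0.05 (alpha/2 = 0.025): 2(1.960 + 0.842)² / 0.16 = 98.1, rounded up to **99**. The t-test gives 99.1.
- Alpha/2 = 0.05 read literally: 2(1.645 + 0.842)² / 0.16 = 77.3, rounded up to **78**.

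The 99 is therefore right for the level in Section 15.3; the printed alpha is not. The attrition step also checks: 125 × 0.8 = 100. At 100 per arm the t-test has 80.4% power, so the claim is correct for the planned sample.

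**2. Apply the same method to 163.** 163/250 = 65% of plan. 163/2 = 81.5 per arm, and 81.5 × 0.8 = 65.2 per arm after 20% attrition. Power is from the two-sample t-test (noncentral t) at two-sided 5%, with noncentrality SMD × √(n/2). At 65.2 per arm this is 0.4 × √32.6 = 2.28; at 81.5 it is 0.4 × √40.75 = 2.55.

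| Attrition | n per arm | Power at SMD 0.4 | SMD detectable with 80% power |
|---|---|---|---|
| Section 15.2 requirement | 99 | 80.0% | 0.40 |
| 0% | 81.5 | 71.8% | 0.44 |
| 10% (assumed) | 73.35 | 67.2% | 0.47 |
| 20% (the plan's rate) | 65.2 | 62.1% | 0.49 |
| 30% (assumed) | 57.05 | 56.3% | 0.53 |

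The normal approximation gives 62.7% at 65.2 per arm and 72.4% at 81.5, so the choice of formula does not matter.

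**3. Allow for baseline adjustment.** Section 15.3 includes baseline pain and PHQ-9 as covariates but gives no correlation. Assume one baseline covariate with correlation r to the 3-month outcome, so that the effective SMD is 0.4/√(1 − r²).

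| Attrition | r = 0.3 | r = 0.5 | r = 0.6 | r needed for 80% |
|---|---|---|---|---|
| 20% | 66% | 74% | 81% | 0.59 |
| 10% | 71% | 79% | 85% | 0.51 |
| 0% | 76% | 83% | 89% | 0.42 |

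**4. What the alpha slip could conceal.** Under the literal two-sided 10% reading, 81.5 per arm exceeds 78 and would have 81.5% power. A reader relying on the printed alpha could conclude that 163 fully followed participants were enough. At the level actually used for testing they are not, in the unadjusted comparison.

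**The case against.** Four points can be made for the plan.

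- **Section 15.2 describes the proposed design.** It is written prospectively, and for 100 analysable per arm it is correct. This stands as far as it goes. However, the section is not marked as historical, it sits in a document that reports 163 randomised, and it draws an unqualified conclusion.
- **62% is conditional, and is not the power of the planned model.** It assumes 20% attrition and no adjustment, while Section 15.3 plans baseline covariates, repeated measures and multiple imputation. This also stands: the power of the planned analysis is unknown from the documents and may reach 80%. But 62% is the like-for-like counterpart of the stated 80%, which was also unadjusted and assumed 20% attrition. Section 15.2 claims no gain from the model. Imputation lets all 163 enter the analysis but does not give unobserved outcomes the information of observed ones, and even 163 fully observed give only 72% unadjusted.
- **The alpha is a slip that changes no number.** Agreed. Section 15.3 settles the intended level and 99 stands. It is the minor part of this point.
- **No test or estimate changes.** True. What changes is a stated property of the trial that readers will use to interpret its results.

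**Conclusion.** The concern holds. With 163 randomised, the power stated in Section 15.2 is not delivered on that section's own assumptions: about 62% at SMD 0.4 instead of 80%, a 38% chance of missing the difference instead of 20%, and a detectable SMD of 0.49 instead of 0.40. This rests on equal arms, 20% attrition, an unadjusted comparison and two-sided 5%. With complete follow-up the unadjusted power is 72%. Adequate power under the baseline-adjusted model is possible but not shown; it needs a correlation of about 0.42 with no attrition, or about 0.59 with 20%. The alpha expression is wrong as printed, but the 99 per arm is right for the two-sided 5% test.

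**What to change.** In Section 15.2:

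- Keep the original calculation if wanted, labelled as the original target, and add a restatement for the 163 randomised with the reason for the shortfall.
- Give the expected analysable number per arm, the unadjusted power at SMD 0.4 (about 62% with 20% attrition, 72% with none) and the detectable SMD (about 0.49 and 0.44). If credit is taken for baseline adjustment, state the assumed correlation, its source and a range.
- Remove or qualify the sentence that power is sufficient for Aims 1 and 2.
- Replace alpha/2 = 0.05 with two-sided alpha = 0.05 (alpha/2 = 0.025); the 99 is unchanged.

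In Section 15.3, add that a non-significant result will be interpreted from its confidence interval against SMD 0.4.

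The cost is protocol and SAP wording, and a less favourable stated power. No further enrolment and no change to the analysis model is proposed.

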## 15.3 Statistical Methods

We will present descriptive statistics. Random effects logistic regression will be used to determine if treatment condition, demographic characteristics, or baseline outcome measures predict study attrition. Any variables that significantly ( $p < .10$ ) predict study attrition will be included in multiple imputation models and as covariates in multivariate models testing the effects of intervention. Graphical methods will be used to evaluate the distributions of outcome variables, examine model residuals, describe change in outcomes over time, and guide the specification generalized linear mixed models testing intervention effects. A 2-tailed probability of Type I error  $< 0.05$  will be used for all null hypothesis tests. Missing data due to participant attrition and item non-response is inevitable. We will conduct intent-to-treat analysis using multiple imputation by chained equation (MICE) to generate fully populated data sets [20]. More specifically we will use the mi impute and mi estimate facilities in Stata 17 to generate and analyze the fully populated data files [21]. The number of imputed data sets will be determined by using the how many imputations procedure [22]. MICE is a flexible tool that allows imputing values for outcomes with a range of distributions (e.g., continuous, dichotomous, count, etc.). MICE assume data are missing at random (MAR) (e.g., missing is random conditional on variables in the imputation model). Variables used in the imputation models will include treatment assignment, all observed instances of the outcome being imputed, and any additional baseline variables found to significantly ( $p < .10$ ) predict subject attrition using mixed-effects logistic regression. Including baseline predictors of attrition supports the MAR assumption.

The BPI, the VAS pain severity scales (worst and average in last week), and the PHQ-9 will be administered at baseline and at all follow-up assessments. The effect of intervention on pain interference (BPI-I), pain severity, and depressive symptoms during the 3-month treatment phase will be evaluated in a generalized linear mixed model framework using the fully populated data sets generated by MICE. Models will include baseline pain and PHQ-9 depression measures as covariates. All available panel data will be included in the model to support the efficiency of estimation. Time specific estimates

of treatment effects (e.g., the effect of treatment at 3-months) can be obtained by including the treatment by categorical (indicator variables) time interaction term. We plan to use the contrast and mimrgns post-estimation commands in Stata to recover relevant parameter estimates and test statistics. More specifically, a Wald  $\chi^2$ -test will be used to test the simple main effect of treatment at end of treatment. Additionally, we will generate graphs plotting the estimated average marginal means to facilitate substantive interpretation of results. Parallel methods will be used to evaluate the sustained effect of treatment post end-of-treatment (4-, 6-, 9-, and 12- months). Wald  $\chi^2$ -tests will again be used to test the simple main effects of treatment at post end-of-treatment assessments to determine if intervention effects are sustained over time.

The Cox proportional hazards model will be used to test the hypothesis that participants randomized to TOPPS will have higher buprenorphine treatment retention than persons randomized to HE. The outcome will be operationalized as self-reported continuous treatment since the prior interview at the time point assessed.

We will use Mplus 7 [23] to specify and estimate structural equation models (SEM) testing the hypothesis that decreased avoidance, and fear of pain mediate the relationship between intervention and pain interference and severity.

Additional baseline covariates will include ratings of pain severity, pain interference, and depression. As recommended by MacKinnon et al. [24], the statistical significance of the indirect effect will be assessed using bias-corrected bootstrapped standard errors. Significant indirect effects are consistent with the hypothesis that change in the purported mechanisms mediates the effect of intervention on outcome.

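### Section 15.3 lets a p < .10 test on attrition, not prognosis, choose the further baseline covariates of the imputation and treatment-effect models; a short list should be fixed in advance

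*Combined protocol and SAP*

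**What the plan says.** The Statistical Methods (Section 15.3) begin with a model for dropout: "Random effects logistic regression will be used to determine if treatment condition, demographic characteristics, or baseline outcome measures predict study attrition". The selection rule follows: any variable that reaches p < .10 in that model "will be included in multiple imputation models and as covariates in multivariate models testing the effects of intervention". The plan rests its missing-data assumption partly on this step: "Including baseline predictors of attrition supports the MAR assumption".

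Some variables do not depend on the screen. For imputation, "Variables used in the imputation models will include treatment assignment, all observed instances of the outcome being imputed". For the outcome analysis, "Models will include baseline pain and PHQ-9 depression measures as covariates". The screen therefore decides only which further baseline variables enter.

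Section 15.3 names no arm-by-variable term in the attrition model and no imputation by arm, though it excludes neither. Section 5 stratifies randomization on enrollment site, disability status and antidepressant use, and Section 15.3 does not name these as covariates. Table 1 shows GAD-7, PASS and drug use in the last 30 days collected at baseline. None of them is fixed as a covariate in the models for pain or PHQ-9.

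**The concern.** The rule filters on one relationship, between the variable and dropout, and has three weaknesses.

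- **Prognosis plays no part.** A variable that predicts 3-month pain but not dropout stays out, and its precision is lost.
- **The primary model is not fixed in advance.** Its covariate set depends on which baseline variables happen to pass p < .10 in the observed dropout data.
- **No arm-by-variable term is named.** If dropout rates are equal, a variable related to dropout in the same way in both arms cancels out of the arm contrast. One related to dropout differently by arm does not, and an overall test has little power when the two arms pull in opposite directions.

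At stake are some precision, a modest possible bias in the TOPPS effect, and a treatment-effect model that cannot be written down before the data are seen.

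**Working it through.** **The plan's own figure.** With SMD 0.4, power 0.80 and two-sided alpha 0.05 (Section 15.3: "A 2-tailed probability of Type I error" below 0.05), n = 2 × (1.960 + 0.842)² / 0.4² = 98.1, so 99 per arm. This matches Section 15.2. The plan gives no operating characteristic for the screen.

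**Inputs from the documents.** 163 randomized (Section 2); 1:1 allocation (Section 5); 20% attrition (Section 15.2, a planning rate, not an observed one). Hence 0.20 × 163 = 32.6, about 33 dropouts, and about 130 analysed, 65 per arm.

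**Assumptions not in the documents.** One extra baseline variable X, standard normal and independent of the baseline outcome; outcome SD 1; coefficient 0.5 for the baseline outcome and 0.3 for X; odds ratios (ORs) for dropout per SD of X as shown; a single dropout indicator.

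**1. How often the screen misses X** (logistic model with arm and X, Wald p < .10, N = 163, 20% dropout per arm, 3,000 runs per cell):

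| Relation of X to dropout | OR 1.5 | OR 2 | OR 2.5 | OR 3 |
|---|---|---|---|---|
| Opposite directions by arm | 89% | 88% | 88% | 87% |
| One arm only | 73% | 51% | 36% | 25% |
| Same direction, half the log-OR in one arm | 54% | 18% | 5% | 2% |

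At the planned N = 250 the opposite-direction row is still 87–89%; the one-arm row falls to 65%, 35%, 16% and 10%.

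**2. Bias in the arm contrast with follow-up outcomes before month 3 ignored** (6,000 simulated trials per setting, screen applied):

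- OR 1.5 in both arms: no bias.
- OR 1.5 in one arm, 1.0 in the other: about 0.02 SD.
- OR 1.5 against 0.67: about 0.05 SD.
- OR 2 against 0.5: 0.07–0.08 SD, which is 18–20% of 0.4.

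Always including X left 0.006 SD or less. If X is never in the model, a wider grid at 20% dropout runs from 0.008 to 0.187 SD. The top needs OR 3 in opposite directions and a coefficient of 0.5, as large as that assumed for the baseline outcome itself.

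**3. Bias once month 1 and 2 outcomes are used, X never included** (assumed residual correlation 0.4–0.6):

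| ORs by arm | All dropouts have months 1–2 | Half have them |
|---|---|---|
| 1.5 vs 1.0 | 0.001–0.007 | 0.010–0.014 |
| 1.5 vs 0.67 | 0.009–0.019 | 0.025–0.032 |
| 2 vs 0.5 | 0.017–0.030 | 0.044–0.052 |

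**4. Precision alone.** Residual SD without X = √(1 − 0.25) = 0.866; with X = √(1 − 0.25 − 0.09) = 0.812. Standard error = SD × √(2/65) = SD × 0.1754, giving 0.1519 and 0.1425. Power = Φ(0.4/SE − 1.96): Φ(0.673) = 75% without X, Φ(0.847) = 80% with it. The difference is about 5 points.

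**5. Would adding an interaction screen be enough?** At N = 163 an arm-by-X test at p < .10 flags an opposite-direction X 64% (OR 1.5) to 95% (OR 2) of the time, but a one-arm X only 26% to 52%. Pre-specifying X does better.

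**The case against.** The strongest reply is that the screen is only a supplement. Arm and every observed value of the outcome are always in the imputation model, and baseline pain and PHQ-9 are always in the outcome model. That stands. A reader might infer that the screen picks the model's covariates as a whole; Section 15.3 does not say so.

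A reader might also infer that the screen usually misses the variables most likely to bias the TOPPS effect. That goes too far, for four reasons.

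- Missing is the rule only for opposite-direction and weak one-arm predictors. At OR 2 in one arm it is about even.
- Differential prediction is not the only source of bias. Equal slopes (OR 2, coefficient 0.3) with 30% against 10% dropout give 0.039 SD, about the same as OR 2 in one arm only (0.040).
- Treating the screen as main-effects only is a reading of silence.
- Imputation from months 1 and 2 removes much of the modelled bias when most dropouts have those visits. The planned screen is also a repeated-measures logistic model, so the miss rates may not carry over exactly.

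Larger power losses can be obtained, but they depend on the sign of the bias. With a bias of 0.02 or 0.05 SD against TOPPS, X omitted gives Φ(0.38/0.1519 − 1.96) = 71% and Φ(0.35/0.1519 − 1.96) = 63%. With the sign reversed, 0.42 and 0.45 give 79% and 84%. Nothing in the documents fixes the sign, so only the precision loss in step 4 can be claimed.

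Nor is chance entry a harm in itself. If 10 independent, unrelated candidates are assumed, at least one passes 1 − 0.9¹⁰ = 65% of the time, but an irrelevant covariate costs little more than a degree of freedom. What remains is that the covariate set is not known in advance.

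None of this supports selecting treatment-effect covariates by an attrition p-value.

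**Conclusion.** The point holds as one of pre-specification and precision, with a modest possible bias. Beyond the fixed variables, covariates are selected by a test that ignores prognosis and is settled only once dropout is known. If a further prognostic variable has a 0.3 SD effect on the outcome, leaving it out costs about 5 points of power with 130 analysed. If it also predicts dropout differently by arm (ORs of 1.5 to 2), the bias is about 0.02 to 0.08 SD in either direction before early visits are used, and smaller after.

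The ORs, coefficients and correlations are assumptions, and 20% is a planning rate. The documents do not show that such a variable exists in this trial or that the TOPPS estimate will be biased. The change is still worth making: with 163 randomized against 250 planned, precision matters, and the better rule costs almost nothing.

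**What to change.** In Section 15.3, before outcomes are examined by arm:

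- Pre-specify a short list of prognostic baseline variables already collected, for example age, GAD-7, PASS and recent drug use, plus the three stratification factors (site, disability status, antidepressant use).
- Enter the list in every imputation and outcome model whatever the p-values, alongside the variables already fixed there.
- Stop letting the attrition p-value choose the covariates of the treatment-effect model.
- Report the attrition regression descriptively, with arm-by-variable terms.

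If outcomes have already been examined by arm, the plan should say so and date the list accordingly. The cost is SAP wording and a few degrees of freedom for covariates that may prove not to be prognostic.
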